Secondary Measures: To better understand factors that may contribute to participant treatment response, the protocol has been expanded to include brief assessments for the following: insomnia, pain, illness intrusiveness, CBT skill acquisition, personality, social support, attachment style, life purpose, and Veterans perceptions. Careful consideration has been taken into selection of the measures, as not to add any undue burden on participants.

Effectiveness Data-Collection Schedule: Data will be collected over 12 months posttreatment to examine long-term effects/decay of the intervention (see Table 3). An initial telephone assessment will screen for exclusion criteria, with final eligibility determined at the baseline appointment. Four-, eight-, and twelve-month follow-up assessments will be conducted by blinded independent evaluators. A 90 minute time limit has been established for all assessment interviews in order to reduce burden on Veteran participants. For participants that do not complete all study measures during the 90 minute assessment period, participants will be

reminded that they have completed their participation. They will be provided with the option to end the call or continue the interview – not to exceed 120 minutes in total time.

Table 3. Assessment Schedule – Effectiveness Data

Aim 1 Effectiveness						
	Screen	Baseline	1 mo (bCBT only)	4 mo (post-tx)	8 mo F/ U	12 mo F/U
Chart Review, Initial PHQ-8, MINI, Cognitive Screen	P-IE or RA					
Demographics		P-IE or RA				
Charlson Index (medical comorbidities)		D				
MINI – depression, anxiety, and PTSD modules		P-IE or RA				P-IE
PHQ-9		P-IE or RA		P-IE	P-IE	P-IE
BDI-II		P-IE or RA		P-IE	P-IE	P-IE
SF-12		P-IE or RA		P-IE	P-IE	P-IE
PCL-5		P-IE or RA		P-IE	P-IE	P-IE
GAD-7		P-IE or RA		P-IE	P-IE	P-IE
Insomnia Severity Index (ISI)		P-IE or RA		P-IE	P-IE	P-IE
Illness Intrusiveness Ratings (Medical Issues)		P-IE or RA		P-IE	P-IE	P-IE
Working Alliance Inventory (Patient)				P-RA*		
Working Alliance Inventory (Clinician)				C-RA		
Cognitive-Behavioral Therapy Skills Questionnaire (CBTSQ)		P-IE or RA	P-RA*	P-RA*		
Ten Item Personality Inventory (TIPI)		P-IE or RA				
Social Support		P-IE or RA		P-IE or RA	P-IE or RA	P-IE or RA
Purpose of Life (PIL)		P-IE or RA		P-IE or RA	P-IE or RA	P-IE or RA
Attachment		P-IE or RA				
VA Perceptions		P-IE or RA		P-IE or RA		
Expectancy Rating Scale (ERS)			P-RA*			
Pain – 2 questions		P-IE or RA		P-IE	P-IE	P-IE
Medication and Health Service Use Database Extraction						D

P-IE = Participant via Independent Evaluator

P-RA = Participant/Research Assistant

D = Database Extraction

C-RA = Clinician/Research Assistant

P-RA* = Participant/Research Assistant - bCBT group only (no usual care)

5.6 Data Analysis

Sample Size and Power Calculations:

Provider Sample (Implementation Data; Aim 1)

No formal sample size calculations were used for the implementation-focused elements of this project. Rather, the team will invite all CBOC providers at all sites within the HOU and OKC VAMCs to participate and subsequently evaluate how many providers opted to engage in the bCBT project. These procedures are common for implementation-focused trials that often have a smaller pool of “subjects”. Designs of this nature often look less at statistical significance and

instead focus more on descriptive quantitative data and depth interviewing and qualitative analyses to determine impact and “lessons learned”.

Veteran Sample (Effectiveness Data; Aim 2)

Sample-size calculations indicate that 232 patients will need to be randomized to address the primary hypothesis for aim 2. Based upon our current project, we will need to recruit 300 Veterans. Approximately 30% of recruited participants were screened ineligible due to subthreshold anxiety and/or depression scores.

We will use unequal randomization to reduce unnecessary recruitment, resulting in 138 patients for bCBT and 94 for EUC. In determining the sample size, we first determined the number of participants needed to have 80% power to detect significant differences in the primary outcomes between our groups. We then inflated this to account for intraclass correlations among patients and for attrition and loss to follow-up. A sample size of 70 patients in both the bCBT and EUC groups (140 total) is needed to detect a difference in the means of the primary outcome that reflects a small effect size of .30, using a 2-sided *t*-test with 80% power at the .05 significance level, adjusted for repeated measures.⁵⁶ The small effect size was chosen to ensure an adequate sample size to address multiple study aims and outcomes. The bCBT sample size was then inflated by $[1 + (m - 1) c]$ to account for the intraclass correlation due to clustering of patients within bCBT clinicians.⁵⁷ Based on the sample size of 70 bCBT patients, an average of 5.8 patients per therapist, and an assumed correlation, *c*, among patients of .10,⁵⁷ our inflation factor is 1.48 ($70 \times 1.48 = 104$). A clustering inflation factor was not used for the EUC group. Both the bCBT and EUC groups are inflated to account for attrition rate at 12 months of 25%.

Unequal numbers of patients per group offers the advantage of reduction in unnecessary recruitment. We will have 80% power to detect a clinically important difference in means on the PHQ-9 between the intervention and usual care groups that is as small as 1.83, based on a small effect size of .30 and estimates of the pooled standard deviation of 6.1.⁵⁸ Lowe concluded that differences in PHQ-9 scores of 5 or greater reflect a clinically relevant difference. Similarly, we can detect differences in the means of the BDI between the treatment and EUC arms as small as 3.6 units, assuming a standard deviation of approximately 12 as seen in [name] et al. 2008.³¹ Assuming mean baseline BDI values of 20 or higher,³¹ we will have more than 80% power to detect a 50% reduction in BDI. For quality of life as measured by SF-12, a difference of one-half standard deviation (i.e., 5 points) is considered clinically significant.⁴⁸ On the basis of the standard deviation of the Mental Component Summary score (MCS) from [name] et al.³¹ of 14.7 and from Hendrick et al of 11.5, we will have 80% power to detect a difference in MCS scores as small as 3.45. For the SF-12 Physical Component Summary score, assuming standard deviations of 11 and 12 we can detect a difference in means as small as 3.3 points. Therefore, we will have more than 80% power to find clinically significant differences in quality of life.

Patient Availability: CBOCs in Houston and Oklahoma City care for a large (n = 50,000+) and diverse Veteran population. We estimate a sample of 7,500 assuming a 15% rate of elevated depressive symptoms.

Minimization of Attrition: Improved engagement and retention of participants may be challenging for Veterans cared for in CBOC settings but our experiences using telephone-based recruitment procedures in prior trials have been highly successful. A 25% attrition rate was used for study-power calculations, which is slightly above our current trial's attrition rate of 22%. Dropouts will include any participants who indicate a desire to withdraw from the study following random assignment. Reasons for study discontinuation will be recorded for subsequent analyses; and overall attrition rates will be examined as a primary study aim. The current proposal employs a flexible intervention approach, using individual sessions and telephone encounters to decrease attrition and improve participant engagement and adherence to treatment. We will also minimize attrition by reducing our "research presence" by using telephone assessments and limited research contact following randomization, and modestly compensating participants for their time. Additionally, Veterans that become difficult to contact via telephone will be mailed an unable to reach letter to encourage them to contact the study (see Appendix 10). The letter will explain the team's efforts in trying to contact them and ask the Veteran to follow up with study staff to schedule an appointment.

Note: bCBT patients who drop out of treatment will be allowed to continue with research follow-up assessments.

Analyses:

Aim 1 analyses will use data from the mixed-method formative evaluation described above.

Quantitative analyses will use descriptive data related to clinician adoption, fidelity ratings, and bCBT utilization (participant engagement, treatment completion, and total session exposure). Data will be compared to our prior work to explore if differences exist between VA hospitals (HOU and OKC) and the CBOCs engaged in the current proposal. We will also use VA databases to explore the use of psychotherapy services pre- and post- implementation using depression ICD-9 and psychotherapy CPT codes as used by the PI in prior work.^{15,59} Qualitative data for aim 2 will use a combined inductive and deductive analytic approach given our desire to understand the firsthand accounts of stakeholders (inductive) while incorporating a priori codes using elements from our implementation frameworks (deductive). The analytic approach will examine interview and field-note data from patients, providers, clinic leaders, and leadership. This entails examining the textual data from the insider's perspective to uncover patterns in the experiences under investigation.^{43, 60-62} The result is the description of a deeper structure, a synthesis of the data into one explanatory framework.⁶² Field notes and transcripts will be read and re-read, and key terms coded. Initial coding will identify significant statements, sentences, or quotes that provide an understanding of how the participants experienced/used bCBT. Study coders will develop clusters of meaning or themes to produce a written description of the contextual elements. Coding will culminate in a codebook that includes a narrative of the central

themes with illustrative quotes, along with a visual portrayal of the data including the factors and outcomes related to the central phenomenon.

The above listed coding methods will be used during the progress-focused formative evaluation. A briefer coding method will be used during other formative evaluation phases. These less rigorous coding strategies, informed by [name] et al, fit well with the focused aims of the formative evaluation phases and are seen as critical to ensure project feasibility. Coding will be conducted by a qualitative investigator at the Houston HSR&D CoE ([name]). [name], a medical anthropologist, will lead the qualitative inquiry. She will collaborate with [name] (senior consultant and co-I) and coordinate coding procedures with the study team.

Aim 2 will determine whether depression and quality of life outcomes differ as a function of the intervention at posttreatment, and at 8- and 12-month follow-ups. All analyses will be done on an intention-to-treat basis. Following the recommendation of the CONSORT group, we will not test for differences in baseline characteristics or adjust subsequent analyses for any variables we did not decide a priori to include in the regression models.⁶³ To compare changes between the 2 groups over time, we will use a longitudinal, mixed-model analysis containing terms for the intercept, treatment, time period and interaction between time and treatment. Separate models will be run for each outcome (PHQ-9, BDI, SF-12 PCS and MCS) and for the combined outcome of whether or not the patient responded to treatment as measured by both a 50% reduction in PHQ-9 and BDI-II. Linear regression will be run for the continuous outcomes and logistic regression will be used for the combined depression outcome. We will include the use of antidepressant medications, receipt of outpatient mental health care, the modality of treatment (e.g., telephone, in-person, combination), and the stratification variable, site, in the analyses to control for any possible differences that might exist between the treatment arms that might impact our outcomes. The interaction between time and treatment will indicate whether there is a difference over time between the 2 groups. We will conduct sensitivity analyses to evaluate whether the reasons for loss to follow-up at the various time periods are related to the observed values of the outcome variable, using tests for missing completely at random and tests for nonrandom missingness.⁵⁶

Analyses for Aim 2 will occur exclusively at the Houston HSR&D CoE under the direction of the PI ([name]), study statistician (Co-I [name]), and study data analyst ([name]).

Other analyses: Prediction of bCBT Treatment Response: We will use multivariate analyses to predict treatment response in the bCBT group, defined as 50% or greater reduction in PHQ-9 and BDI scores from baseline to posttreatment. Variables will include patient demographic and clinical characteristics (e.g., baseline depression severity, mental health comorbidities, treatment expectancy), as well as treatment (number of sessions attended, therapeutic alliance, patient engagement) and clinician factors (e.g., clinician adherence/skillfulness). Depression Treatment Intensity: Within the bCBT treatment group, the study team will evaluate the associations between depression-symptom response and treatment intensity (number of sessions). We will explore potential patient demographic and clinical characteristics associated with treatment response and intensity. Further, we will use surveys and qualitative interviews

with clinicians and bCBT participants to more fully understand whether the treatment intensity received was the treatment believed to be ideal. Perspectives from both patients and providers will be needed to fully understand this construct.

All exploratory analyses will occur exclusively at the Houston HSR&D CoE under the direction of the PI ([name]), study statistician (Co-I [name]), and study data analyst ([name]).

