The bCBT intervention will be delivered by VA CBOC clinicians at the Houston and Oklahoma City affiliated CBOCs. All mental health clinicians at the 16 CBOC sites will be approached for inclusion in the study. We anticipate that a minimum of 12 clinicians will be enrolled, with a realistic estimate to approach 15 or more enrolled clinicians before the end of the trial, given staff turnover and program expansion efforts. Clinicians will receive online bCBT training with an emphasis on care for Veterans in the CBOC setting. Clinicians will be invited to participate by referral from clinic directors and/or VISN 16 mental health leadership. The study team will follow-up with the clinician and his/her supervisor to verify that study participation is appropriate. CBOC clinicians will receive advocacy (when needed) from the study staff and VISN leadership (see Appendix 2, letters of support) to resolve barriers to participation. Clinicians will not be restricted based on discipline or prior CBT experiences, but will be expected to have an interest in obtaining training and willingness to use bCBT in their practice. As seen in our ongoing trial, we anticipate that nurses, social workers, psychologists, counselors, and physician assistants will participate. The study team will try to work with clinicians to receive workload credit, but will not guarantee.

All enrolled clinicians will receive a series of training and facilitation tools to assist their use of bCBT in their VA care settings. The proposed implementation strategy (training and facilitation tools) will be based on our prior work as outlined by Mignogna, et al. 2014.²² The proposed implementation strategy will initially include a series of techniques but will be modified with input from CBOC stakeholders during the development and refinement process. The initial strategy will include the following facets:

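### At equal power the 138:94 allocation is not shown to save any recruitment, and with 12 to 15 therapists it falls short of the stated 80% power

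*Combined protocol and SAP*

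**What the plan says.** The Veteran sample part of Section 5.6 sets the total: "Sample-size calculations indicate that 232 patients will need to be randomized to address the primary hypothesis for aim 2". It starts from an unclustered requirement: "A sample size of 70 patients in both the bCBT and EUC groups (140 total) is needed", for a difference that "reflects a small effect size of .30", with "80% power at the .05 significance level, adjusted for repeated measures". The bCBT arm alone is then multiplied by 1.48 for clustering of patients within clinicians (5.8 patients per therapist, intraclass correlation 0.10), and both arms are inflated for 25% attrition.

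The ratio is justified once with "We will use unequal randomization to reduce unnecessary recruitment, resulting in 138 patients for bCBT and 94 for EUC" and again with "Unequal numbers of patients per group offers the advantage of reduction in unnecessary recruitment". The documents give no other reason for it and show no comparison with an equal split.

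On therapist supply, Section 5.1 (Study Aim #1) states: "We anticipate that a minimum of 12 clinicians will be enrolled". It calls 15 or more realistic. Section 5.3 counts 24 mental health clinicians serving the 16 clinics.

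**The concern.** Inflating one arm for clustering makes that arm larger, but it does not follow that the resulting ratio needs fewer patients than 1:1. The relevant comparison is an equal split with the same power, and the plan does not make it.

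A second issue sits behind the ratio. The factor of 1.48 assumes a caseload that fits 70 bCBT patients, whereas the design randomises 138 and expects about 104 to be evaluable. Unless more therapists join, the caseload and the design effect rise. The stated reason for a core design choice and the stated power are both at stake.

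**Working it through.** **Inputs.** From Section 5.6: 70 per arm before inflation, m = 5.8, c = 0.10, no clustering factor in EUC, 25% attrition. From Section 5.1: 12 therapists at minimum, 15 or more expected. From Section 5.3: 24 in post.

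**Plan's figure reproduced.**
- Factor: 1 + (5.8 − 1) × 0.10 = 1.48.
- bCBT: 70 × 1.48 = 103.6, and 103.6/0.75 = 138.1 (stated 138).
- EUC: 70/0.75 = 93.3 (stated 94).
- Total: 232, as stated.

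The base of 70 cannot be rebuilt from what is stated. An effect of 0.30 without a repeated-measures adjustment needs 175 per arm, and the within-patient correlation is not given. I therefore take as given that 70 v 70 unclustered patients yield 80% power. The missing adjustment scales both allocations alike, so it does not affect their comparison.

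**Scale.** With evaluable numbers n1 (bCBT) and n2 (EUC), the variance is proportional to V, and the target is 2/70 = 0.02857. Power = Φ(2.8016 × √(0.02857/V) − 1.96).

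**Comparison 1: the plan's fixed factor, V = 1.48/n1 + 1/n2.**
- 138:94 (103.5 and 70.5 evaluable): V = 0.02848, power 80.1%.
- 116:116 (87 and 87 evaluable): V = 2.48/87 = 0.02851, power 80.1%.

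The tie is algebraic. For ratio k = n1/n2 and design effect D, the required total is proportional to (1 + k)(1 + D/k). This equals 2(1 + D) both at k = 1 and at k = D. The plan sets k at about D, so both ratios need 2 × 2.48/0.02857 = 173.6 evaluable, or 231.5 randomised.

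Inflating both arms gives 2 × 104/0.75 = 277. Then V = 2.48/104 = 0.02385 and power is 86.6%, above the target.

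**Comparison 2: J therapists, with J not depending on bCBT enrolment.** The factor becomes 1 + (n1/J − 1) × 0.10, so V = 0.9/n1 + 0.1/J + 1/n2.

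| J | 138:94, patients per therapist | 138:94, factor | 138:94, power | 116:116, power |
|---|---|---|---|---|
| 12 | 8.6 | 1.76 | 76.4% | 77.8% |
| 15 | 6.9 | 1.59 | 78.7% | 80.1% |
| 18 | 5.75 | 1.475 | 80.2% | 81.6% |
| 24 | 4.3 | 1.33 | 82.1% | 83.6% |

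Example, J = 12: 138:94 gives 0.9/103.5 + 0.1/12 + 1/70.5 = 0.03121, and 116:116 gives 1.9/87 + 0.1/12 = 0.03017.

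Under this model an equal split of about 222 patients matches 138:94 at 232.

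**Source of 5.8.** 70/12 = 5.83, the arm before inflation over the minimum number of clinicians. With 104 evaluable bCBT patients, a caseload of 5.8 needs 104/5.8 = 17.9, so about 18 therapists.

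**The case against.** The recruitment sentences name no comparator. The same paragraph says that the EUC arm was not inflated for clustering, so the natural reading is that the plan avoided enlarging EUC as well. Against that design 138:94 does recruit about 45 fewer patients (277 − 232). This stands, and a reader who infers that the rationale is simply false goes too far. It fails only at equal power.

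A reader might also infer that 138:94 tilts the wrong way. That holds only if therapist numbers do not grow with bCBT enrolment, in which case the best ratio is √0.90 = 0.95:1. The plan expects 15 or more clinicians with turnover and programme expansion, and 24 are in post, so 18 is not out of reach. With the factor held at 1.48 the best ratio is √1.48 = 1.22:1, at about 230 randomised, which does favour bCBT and saves two or three patients. With 5.8 per therapist held, a correlation of 0.15 favours 138:94 (77.0% v 76.4%) and 0.05 favours 116:116 (83.9% v 83.3%). The direction depends on the model.

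The loss is also small, about 1.4 points. At 12 therapists an equal split recovers 1.4 of the 3.6-point shortfall and still misses 80%; the larger part comes from the caseload assumption. Finally, extra bCBT patients serve the Aim 1 engagement and utilisation data and the bCBT-only analyses. That could justify the ratio, although the plan does not say so.

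**Conclusion.** The concern holds in a limited form. The only reason given for 138:94 is not supported at equal power: on the plan's own factor, 116:116 needs the same 232 patients for the same 80.1%. If therapist numbers are set by who enrols, 138:94 costs about 1.4 points relative to 116:116 and gives 76.4% to 78.7% at 12 to 15 therapists, reaching 80% at about 18.

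These figures assume that 70 v 70 gives 80% power, a correlation of 0.10, 25% attrition in both arms, no clustering in EUC, and caseload counted in evaluable patients.

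The documents do not support concluding that the allocation materially damages the trial or that it has to be changed to 1:1. What needs correcting is the rationale and the power statement.

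**What to change.** - Delete both recruitment-saving sentences in Section 5.6.
- If 138:94 is kept, state the actual reason, for example more bCBT patients for Aim 1 and the bCBT-only analyses.
- Recompute the clustering factor from the inflated bCBT arm and the expected number of therapists, and report the resulting power: about 76% at 12, 79% at 15 and 80% at 18.

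This costs wording only and adds no patients.

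If the ratio can still be changed, 116:116 at the same total gains about 1.4 points with therapists fixed. The price is 22 fewer randomised and about 17 fewer evaluable bCBT patients (104 to 87) for Aim 1 and the exploratory analyses. The document is dated January 2018 and Section 6.0 anticipated first enrolment in March 2015, so this option may no longer be practical; the corrections above apply either way.

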All randomized participants will also receive a note added to their charts. The note will provide information about the patient's level of depressive symptoms, the presence or absence of suicidal ideation reported, and any actions being taken by the research team. Notes will provide information about the assessment process, including information conveyed to the subject about the VA crisis hotline and encouragement provided to the patient to seek additional services through their existing care providers. The note will also indicate that the patient should continue to receive care as usual regardless of their study group assignment. Participants randomized to bCBT will receive a note, similar to the EUC group, with the exception being that the note will also indicate the patient was referred to a local CBOC provider for bCBT care. For subjects that enter the trial with depression but without suicidal ideation, the study team intends to provide a

detailed note for the chart but will NOT require an additional signature or co-signature from the PCP.

The primary outcome, depression symptoms, will be evaluated at 4-, 8- and 12-month follow-ups.

Study Aim #1: Implementation (Training and Assistance Program) of bCBT by CBOC clinicians

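### Depression symptoms are the named primary outcome, but no scale, visit or matching contrast is fixed, and no multiplicity rule is given

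*Combined protocol and SAP*

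**What the plan says.** - **Section 5.1, Study Design:** "The primary outcome, depression symptoms, will be evaluated at 4-, 8- and 12-month follow-ups". This fixes a domain and three visits, but no scale and no deciding visit.
- **Section 5.5, Effectiveness Measures:** the domain is measured with PHQ-9 and BDI-II. BDI-II is described as the second of the two, but the text does not say which one decides. bCBT clinicians also give PHQ-9 during treatment, while only study personnel give BDI-II.
- **Section 5.6, Sample Size and Power Calculations:** the aim is "80% power to detect significant differences in the primary outcomes between our groups". The base calculation reads "A sample size of 70 patients in both the bCBT and EUC groups (140 total) is needed", for a difference in means that "reflects a small effect size of .30", "using a 2-sided" t-test "with 80% power at the .05 significance level". Detectable differences for PHQ-9, BDI, MCS and PCS follow from the same calculation.
- **Section 5.6, Analyses (Aim 2):** "Separate models will be run for each outcome (PHQ-9, BDI, SF-12 PCS and MCS", plus a fifth, logistic model for combined response on both depression scales. A group difference over time is to be read from the time-by-treatment interaction. No analysis alpha, deciding visit, hierarchy or adjustment is given.
- **Section 3.0, Objectives:** Aim 2 lists PHQ-9, BDI and SF-12 together, without ranking them.

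**The concern.** A sample size at .05 describes the false-positive risk of one test. When two scales stand for the primary domain and nothing says which one decides, that risk is larger than .05, and the choice can be made after the results are seen.

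The choice of scale is not neutral. bCBT participants meet PHQ-9 in their sessions and EUC participants do not, so the two scales could give different answers.

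The contrast is open as well. The power text concerns a difference in means. The analysis text points to an interaction and does not say whether baseline is one of the model's time periods, how time is coded, or whether the interaction is tested jointly. If only follow-up visits enter, a steady benefit at 4, 8 and 12 months would appear in the treatment term and leave the interaction near zero. If baseline enters, the benefit would appear in the interaction, but through a test with a different power basis from the t-test.

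**Working it through.** **1. The plan's own figure.** Inputs from section 5.6: 70 per arm, 5.8 patients per therapist, correlation .10, and 25% attrition.
- bCBT: 70 × [1 + (5.8 − 1) × 0.10] = 70 × 1.48 = 103.6; 103.6 / 0.75 = 138.1, stated as 138.
- EUC: 70 / 0.75 = 93.3, stated as 94.
- Total: 138 + 94 = 232, as stated.

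The base of 70 depends on a repeated-measures adjustment whose within-patient correlation is not given, so that step cannot be confirmed. No step allows for more than one outcome.

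**2. One undivided .05 for every powered scale.** Each detectable difference is 0.30 SD:
- PHQ-9: 0.30 × 6.1 = 1.83
- BDI: 0.30 × 12 = 3.6
- MCS: 0.30 × 11.5 = 3.45
- PCS: 0.30 × 11 = 3.3

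The same 0.30 at 80% power for all four means that none of them was given a smaller alpha.

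**3. Chance of at least one false positive under no effect.** For k independent tests this is 1 − 0.95^k two-sided, and 1 − 0.975^k counting only results in favour of bCBT.
- k = 2: 9.75% and 4.9%
- k = 5: 22.6% and 11.9%

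The outcomes are correlated, and the documents give no correlations. The table assumes a common correlation and comes from simulated multivariate-normal test statistics (500,000 draws per cell, two-sided .05 each).

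| Outcomes that can carry the claim | Correlation 0.3 | 0.5 | 0.7 |
|---|---|---|---|
| Two depression scales, either direction | 9.6% | 9.0% | 8.3% |
| Two depression scales, favouring bCBT | 4.8% | 4.5% | 4.2% |
| All five models, either direction | 21.0% | 18.4% | 14.8% |
| All five models, favouring bCBT | 10.5% | 9.2% | 7.4% |

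The single-test reference is 5% in either direction and 2.5% favouring bCBT. At correlation 0.8 the two-sided figures fall to 7.8% (two scales) and 12.8% (five models).

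A common correlation fits the combined response poorly, because it is built from the two scales. With unequal correlations (PHQ-9 with BDI 0.6-0.8, PCS only weakly related to the rest) the five-model figure is 17-20%, inside the same range.

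**The case against.** The plan is less open than a quick reading suggests, and several stronger inferences fail.

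- **That no primary outcome or test is named.** Section 5.1 names the domain, and section 5.6 also uses the singular for the primary outcome. PHQ-9 sets eligibility, and BDI-II is called second, which leans towards PHQ-9 but may only mean additional. Section 5.6 does name a test, the interaction. What remains open is the scale, the visit and the match to the powered contrast.
- **That the risk is 15-21%.** This needs SF-12 or combined response alone to count as effectiveness. Section 3.0 puts quality of life under Aim 2 and nothing labels it secondary, so that reading is not excluded. But it is not stated, and section 5.1 confines the primary outcome to depression.
- **That 15-21% is the chance of a false claim of benefit.** The figure counts both directions. Benefit alone is 7-11%.
- **That three visits multiply the tests.** Reading five outcomes at each of three visits would give about 34-44% (unequal between-outcome correlations, between-visit correlation 0.5-0.7). The plan does not specify visit-by-visit tests, and a joint interaction test is one test per outcome. This figure should not be used.
- **That attrition adds another primary test.** Section 5.6 says "overall attrition rates will be examined as a primary study aim". This is loose labelling, absent from the aims in section 3.0, and it cannot yield a claim of effectiveness.

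It is also fair to say that .05 per model is inferred from the power text, since the analysis text states no level. None of this supplies the missing scale, contrast or rule.

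**Conclusion.** The concern stands in a limited form. The primary domain is named, but the deciding scale and visit are not. The named interaction test differs from the powered difference in means, and nothing controls error across outcomes that the power text itself treats as plural. The relevant size is about 8-10% two-sided if either depression scale can carry the claim. The larger five-outcome range is conditional on a decision rule that the plan leaves unsaid. Both sizes rest on assumed correlations of 0.3-0.7 and on testing each outcome at .05. This should be settled before the arms are compared. It does not put the recruitment target in question.

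**What to change.** Amend the Aim 2 analysis text before unblinding:

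1. Name one depression scale as primary and give the reason. PHQ-9 sets eligibility and comes first in the power text. BDI-II is free of in-session use by bCBT clinicians.
2. Name one contrast that matches the powered difference in means, for example the baseline-adjusted average over 4, 8 and 12 months, tested at two-sided 0.05. Let it replace the unspecified interaction as the deciding test.
3. If both scales stay primary, apply Holm to the two.
4. Label the remaining outcomes secondary, and report visit-specific effects as estimates with intervals. Formal adjustment across the secondary outcomes is a matter of preference.

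**Cost.** The change is to wording, with no extra patients if one scale is chosen. A significant result on a non-primary outcome alone can no longer be presented as the Aim 2 answer.

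Holm on two scales costs some power when only one scale truly responds, because that scale must then usually pass .025. For a test planned at 80%, power becomes Φ(1.960 + 0.842 − 2.241) = Φ(0.561), about 71%. Restoring 80% at .025 would take (2.241 + 0.842)² / (1.960 + 0.842)², about 1.21 times the sample. Naming a single scale avoids this.
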